## DOCUMENT CHANGE HISTORY

Version date	Author	Description of change(s)
31jul2019	[REDACTED]	Original protocol

### **Disclaimer**

This study will be conducted for research purposes only and is not intended to be used to support safety and efficacy in a regulatory submission.

## 1 INTRODUCTION

The worldwide prevalence of dry eye is estimated to be approximately 5% to 50%. Dry eye is classified into three main subtypes: aqueous deficient, evaporative, and mixed. In order to effectively treat patients, it is important for eye care practitioners to be able to differentiate between the different causes of dry eye.

One non-invasive method of assessing the rate of evaporation of the tear film from the front surface of the eye is by using a technique called evaporimetry. At present, there is only one commercial evaporimeter, the Eye-VapoMeter (Delfin Technologies Ltd., Finland), available for clinical use. The Eye-VapoMeter was initially designed as a dermatological device to measure the rate of skin evaporation. The device was modified by incorporating an eye cup from a swimming goggle onto the base of the instrument and was validated for ocular use in 2014.

All other evaporimeters previously described in the literature have only been used within a research setting. To our knowledge, there has only been one previous evaporimeter, developed by Tsubota and Yamada in 1992, which was capable of binocularly measuring the tear evaporation rate (TER).

The 2017 TFOS DEWS II Tear Film report noted that there is currently a lack of reliable, commercially available evaporimeters and stressed that the development of evaporimeters that can be used in a clinical setting under a variety of temperatures and humidities would be extremely useful. To overcome various problems associated with the Eye-VapoMeter and the Yamada/Tsubota evaporimeter, a novel, prototype goggle-based evaporimeter has been designed to simultaneously measure TER from both eyes at the same time. The benefit of a simultaneous TER measurement is less chair time for both the patient and practitioner.

Due to the relative lack of previously published research investigating evaporimetry and eye drops, the purpose of this pilot study is to compare the effect of an eye drop (Systane® Complete) on TER. Systane® Complete was released in Canada in 2018 for the treatment of both aqueous deficient and evaporative dry eye. The study will also serve to validate the use of the novel, in-house developed evaporimeter for use in non-contact lens wearing participants.

## 2 OBJECTIVES

The objective of the study is to compare the rate of tear evaporation, measured with a novel evaporimeter, before and for one hour after an eye drop containing nano-sized oil droplets has been instilled.

The primary outcome variable for this study are the slopes calculated from the change in relative humidity over time.

Other variables of interest include:

- Ocular Surface Disease Index (OSDI) score
- Comfort (subjective rating)
- Dryness (subjective rating)
- Burning/stinging (subjective rating)
- Tear meniscus height (mm)
- Non-invasive Keratograph® break up time (NIK BUT)
- Lipid layer thickness (TearScience LipiView® II)
- Ocular surface area (mm^2)
- Volume inside the goggle (cm^3)

### 3 HYPOTHESIS

The study hypothesis is that instillation of an eye drop will result in lower tear evaporation rates compared to before the eye drop has been inserted.

The second study hypothesis is that dry eye participants will have higher baseline rates of tear evaporation compared to non-dry eye participants.

### 4 MATERIALS AND METHODS

[figure not shown]
#### 4.1 STUDY DESIGN

##### 4.1.1 OVERALL DESIGN

This is a prospective, bilateral, non-dispensing, non-randomized pilot study that will seek to successfully complete 10 dry eye and 10 non-dry eye participants who do not wear contact lenses. More participants are likely will be screened due to the potential for screen failure. The study will involve 2 scheduled visits over 2 days.

Visit 1: Screening visit

Visit 2: Data collection, including instillation of the study eye drop

#### 4.1.2 RANDOMIZATION

---

There will be no randomization in this study.

#### 4.1.3 MASKING

---

There will be no masking in this study.

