#### 4.5.5 TEAR MENISCUS HEIGHT (TMH)

---

The participant will be seated in front of the OCULUS Keratograph® 5M (K5M) with their chin on the chin rest and head against the forehead rest. The investigator will select the Tear Meniscus Height feature from the TF-Scan section on the K5M. The infrared (IR) illumination setting will be used. The camera will be adjusted so the tear meniscus is in the centre of the image. The device will project rings of light (Placido discs) onto the tear film. The participant will be instructed to look straight ahead and an image of each eye will be taken. TMH will be calculated as the average of two measures taken using the on-screen calipers.

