#### 4.5.12 ANTERIOR EYE PHOTOGRAPHS

---

The participant will be seated at a Zeiss slit lamp attached to a Canon EOS 60D digital camera. A photograph of each eye will be taken at 5x magnification with additional external illumination provided by a Canon Macro Twin Lite flash. The participant will hold a ruler underneath each eye while the photographs are taken. The ruler will serve as a calibration reference when the images are analysed with ImageJ in order to determine the size of the ocular surface in mm^2. The ruler will be cleaned with an alcohol wipe prior to being given to each participant.

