#### 4.5.18 EVAPORIMETRY

---

The participant will be seated at an adjustable height table and will place their elbows on the table. The participant will hold a pair of modified swimming goggles (Figures 1A and 1B) over their eyes for 20 seconds while their eyes are open. The participant will be prompted to blink every 3 seconds during the measurement using a metronome (<https://www.youtube.com/watch?v=9ypeNJJeKIs>). The goggle will be removed and ventilated in front of a fan until the relative humidity returns to baseline levels. The goggle will then be placed over the eyes for 20 seconds while they are closed to measure the evaporation rate from the skin. Three consecutive measurements of open eye and closed eye measurements will be taken. Recordings of the temperature and relative humidity during the measurement will be saved as a word document and images of the temperature and

humidity versus time plotted as a graph will be saved as a png file. The rate of tear evaporation will be calculated from slope derived from the change in relative humidity over time. The evaporation rate from the ocular surface will be calculated by subtracting the evaporation rate of closed eye from the evaporation rate of the open eye. The average of three ocular surface evaporation rates will be calculated for each eye.

[figure not shown]

Figure 1: (A) Evaporimeter with arrows showing the location of the temperature/humidity sensors in the swimming goggles. (B) View of the front of the evaporimeter.

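### Primary humidity slopes may be derived with group and time point known: no masking is planned and no fitting or trace-rejection rule is fixed

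*Combined protocol and SAP*

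**What the plan says.** - Section 4.1.3: "There will be no masking in this study". No other section provides for coded files, a separate reader or a masked analysis. Section 4.1.2 adds "There will be no randomization in this study", and only one product is studied, before and after instillation.
- Section 2: "The primary outcome variable for this study are the slopes calculated from the change in relative humidity over time".
- Section 3: "The study hypothesis is that instillation of an eye drop will result in lower tear evaporation rates compared to before" the drop, and "The second study hypothesis is that dry eye participants will have higher baseline rates of tear evaporation compared to non-dry eye participants". Both hypotheses concern tear evaporation rate and both state a direction.
- Section 4.5.18: each goggle application lasts 20 s. Three open-eye and three closed-eye measurements are taken, and the humidity and temperature recordings and their graphs are saved as files. "The rate of tear evaporation will be calculated from slope derived from the change in relative humidity over time". The closed-eye rate is subtracted from the open-eye rate, and three such differences are averaged for each eye. The section names no fitting window, regression method, criterion for rejecting or repeating a trace, or reader.
- Table 4 in section 10.1 adds only that the statistic is a slope. Analysis is in-house, with Excel, GraphPad and SPSS named for the data as a whole.
- Two secondary variables also involve manual reading. For meniscus height, section 4.5.5 says "TMH will be calculated as the average of two measures taken using the on-screen calipers". For ocular surface area, section 4.5.12 says "The ruler will serve as a calibration reference when the images are analysed with ImageJ".

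**The concern.** When a reader turns a trace into a slope, someone must decide where the fit starts and stops and whether a disturbed trace counts. If those decisions are made trace by trace, by someone who knows whether the trace is before or after the drop and whether the participant has dry eye, they can drift towards the expected answer. The design has no control drop or randomized comparison against which such drift would cancel.

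The slopes matter beyond description, even in a pilot. They are tested at p < 0.05 (section 4.2.1). They feed the analysis that sets the final sample size (section 10.1) and inform the sizing of future studies (section 4.2.1). They are also part of the validation of the new evaporimeter (section 1). The double data entry in section 12 detects transcription errors. It does not detect a choice made while the slope was being derived.

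**Working it through.** The plan states no effect size, standard deviation, reader error or power, so there is no figure of its own to reproduce. Three checks follow. The second and third are illustrations on stated assumptions.

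**1. What the recordings allow.** Section 4.5.18 gives 3 open-eye and 3 closed-eye measurements for each of two eyes. Section 4.5.17 and the Visit 2 schedule give 5 time points (two baselines, then 10, 30 and 60 minutes). Per participant this is 6 × 2 × 5 = 60 traces. For 20 completers it is 60 × 20 = 1,200 traces. All are saved, so they can be coded and fitted away from the visit.

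**2. How far the window alone can move a slope.** Assume that goggle humidity rises as f(t) = 1 − exp(−t/τ), up to a scale factor. The least-squares slope over 0 to T is

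b(T) = (12/T³) ∫₀ᵀ (t − T/2) f(t) dt.

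The time constant τ is not in the documents, so a range is shown:

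| τ (assumed) | b(5 s) | b(10 s) | b(20 s) | b(10)/b(20) | b(5)/b(20) |
|---|---|---|---|---|---|
| 10 s | 0.0784 | 0.0622 | 0.0406 | 1.53 | 1.93 |
| 20 s | 0.0442 | 0.0392 | 0.0311 | 1.26 | 1.42 |
| 40 s | 0.0235 | 0.0221 | 0.0196 | 1.13 | 1.20 |

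A window that differs between traces can thus change a slope by 13% to 53% (0-10 s against 0-20 s) or by 20% to 93% (0-5 s against 0-20 s). If the same window is used on every trace, all slopes with the same τ change by the same ratio and no comparison is favoured. Bias requires a mixture that differs by group or time point. For example, with τ = 20 s, using 0-10 s on one in four baseline traces and 0-20 s on all others would raise the mean baseline slope by about 0.25 × 26% = 6.5%, and the drop would appear to lower evaporation. The model describes a single trace. The analysed quantity is the open-minus-closed difference averaged over three pairs, for which the ratio carries over only if both traces of a pair share window and τ.

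**3. What a systematic shift does to the nominal 0.05.** Take two-sided t-tests with no true effect and a reading shift of δ standard deviations. The noncentrality is δ√20 for a paired before/after test with n = 20 (19 degrees of freedom), and δ/√(2/10) for 10 against 10 (18 degrees of freedom).

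| δ (assumed) | Paired, n = 20 | Dry vs non-dry, 10 vs 10 |
|---|---|---|
| 0 | 0.050 | 0.050 |
| 0.1 | 0.071 | 0.055 |
| 0.2 | 0.136 | 0.071 |
| 0.3 | 0.247 | 0.097 |
| 0.5 | 0.565 | 0.185 |

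δ is in units of the SD of paired differences in the first column of results and of the between-person SD in the second. The before/after contrast is the more sensitive. Sidedness is not stated in the plan; two-sided is assumed.

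**The case against.** The strongest reply is that this is an open, one-product pilot with 20 completers. The disclaimer before section 1 says it is not meant to support safety and efficacy in a regulatory submission, and participants and examiners could not realistically be masked. That stands for the visit, and it lowers the severity. It does not explain leaving derivation from saved files unmasked.

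A second reply is that every recording lasts 20 s, so fitting the whole trace is the natural reading and leaves little discretion. This is plausible but not written, and it says nothing about disturbed traces.

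A third is that a scripted fit with a fixed window removes most of the discretion by itself, so that masking then adds little. This largely stands. Coding still protects any rejection decision that a script cannot fully settle, and it costs little once a script exists.

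A fourth is that the percentages above measure the effect of changing windows, not of knowing the group. That is correct. They show how much room for judgement exists, not how much bias will occur.

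**Conclusion.** The gap is real and concerns the primary outcome. Masking is excluded outright, the slopes come from saved recordings with no fixed window or rejection rule, and both hypotheses on that outcome are directional with no control arm. It is worth correcting, but it is not a fatal flaw in a pilot. The size is unknown. The 13% to 53% range rests on an assumed curve and on windows that vary between traces, and the error rates rest on assumed shifts.

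The documents do not support several stronger readings that a reader might infer:

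- **That meniscus height and ocular area share this problem as outcomes behind the hypotheses.** Section 3 concerns evaporation rate only. In Table 4 these two variables enter only as correlates of it.
- **That ocular area is read with time point known.** Photographs are scheduled at Visit 1 only (section 4.4.2 and Table 3), before any drop, so at most group is known.
- **That meniscus height is read later from saved files.** Section 4.5.5 describes on-screen calipers and does not say when they are used.
- **That the plan states the analyst will know group and time point.** This is a fair inference from section 4.1.3, but it is not written.
- **That window choice could outweigh the effect of the drop.** The documents give no expected effect to compare it with.

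**What to change.** In section 4.1.3, replace the blanket statement with text to this effect: participants and examining investigators are not masked; saved humidity recordings are stored under random codes so that group and time point are hidden while slopes are derived; codes are opened after the derived dataset is locked.

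In section 4.5.18, state one fitting window, one regression method and one objective trace-rejection rule, all set before any Visit 2 trace is fitted and applied by script to every open-eye and closed-eye trace. Report the number of traces rejected by group and time point.

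As a secondary step, code the ocular photographs (to hide group) and the meniscus images in the same way wherever they are read offline. Break-up time and LipiView thickness are produced by the instruments and need this less.

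The cost is a short script to rename files and fit slopes, and a small delay before derived values are linked to group and time. With about 1,200 traces, scripted fitting is probably less work than fitting by hand. Visits, participant burden and sample size do not change. The change does not remove bias at acquisition: participants hold the goggle themselves, and they and the examiner know whether the drop has been given.

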### 4.2 STUDY POPULATION

#### 4.2.1 SAMPLE SIZE CALCULATION

---

Because this is a pilot study, a sample size calculation has not been completed. Results from this study will help with sample size determination for future studies.

A *p*-value of < 0.05 will be considered statistically significant.

#### 4.2.2 NUMBER OF PARTICIPANTS

---

Up to 60 participants will be recruited / screened using CORE records and advertising approved by the UW Office of Research Ethics, with a target of 10 dry eye and 10 non-dry eye participants completing the study. At least 20 participants will have the study product instilled at Visit 2. Informed consent will be obtained for all participants prior to their enrolment in the study.

#### 4.2.3 INCLUSION AND EXCLUSION CRITERIA

---

A person is eligible for inclusion in the study if he/she:

1. Is at least 18 years of age and has full legal capacity to volunteer;
2. Has read and signed an information consent letter;

3. Is willing and able to follow instructions and maintain the appointment schedule;
4. Is willing to be awake for at least 2 hours before visit 2;
5. Is willing not to wear eye makeup on the day of visit 2;
6. Is willing not to use eye drops or artificial tears on the days of visits 1 or 2;
7. Group specific criteria:
  - a. Dry eye participant group: Symptoms: OSDI  $\geq$  13 and Signs: NIKBUT  $\leq$  5 s in the worst eye
  - b. Non-dry eye participant group: Symptoms: OSDI  $<$  13 and Signs: NIKBUT  $\geq$  10 s in the worst eye

A person will be excluded from the study if he/she:

1. Is participating in any concurrent clinical or research study;
2. Has any known active\* ocular disease and/or infection;
3. Has a systemic condition that in the opinion of the investigator may affect a study outcome variable;
4. Is using any systemic or topical medications that in the opinion of the investigator may affect a study outcome variable;
5. Has known sensitivity to sodium fluorescein dye;
6. Is pregnant, lactating or planning a pregnancy at the time of enrolment (by verbal confirmation at the screening visit);
7. Is aphakic;
8. Has undergone refractive error surgery;
9. Has undergone ocular surgery in the last 6 months;
10. Has punctal plugs;
11. Has a known sensitivity to Systane® eye drops (including Systane® Balance, Systane® Complete, Systane® Gel Drops, Systane® Ultra, etc.)
12. Has a known sensitivity to petroleum jelly (Vaseline);
13. Has epilepsy and/or sensitivity to flashing lights;
14. Has worn contact lenses within the past month or is planning to wear contact lenses during the study;
15. Has any physical impairment that would interfere with holding the evaporimeter;
16. Has taken part in another clinical research study involving ocular drops or treatments within the last 14 days;

\* For the purposes of this study, active ocular disease is defined as infection or inflammation which requires therapeutic treatment. Mild (i.e. not considered clinically relevant) lid abnormalities (blepharitis, meibomian gland dysfunction, papillae), corneal and conjunctival staining and dry eye are not considered active ocular disease. Neovascularization and corneal scars are the result of previous hypoxia, infection or inflammation and are therefore not active.

#### 4.2.4 REPEATED SCREENINGS

---

In some circumstances a repeated screening may need to be scheduled. Examples include, but are not limited to:

1. Incomplete information available at time of screening to determine eligibility (e.g. history from current eye care practitioner etc.)
2. Study procedures unable to be completed in time scheduled for visit;
3. Study products not available at the time of the screening visit;
4. A transient health condition which may affect the eye(s) (e.g. a common cold, active allergies, fatigue etc;)
5. The short term use of medications (e.g. antibiotics, antihistamines etc.)
6. Reassessment of baseline ocular conditions (e.g. corneal and/or conjunctival staining, scars etc.)

The maximum total number of screenings permitted will be 2 (i.e. 1 repeated screening is allowed).

### 4.3 STUDY MATERIALS

#### 4.3.1 LENSES

---

No lenses will be dispensed in this study.

#### 4.3.2 LENS CARE SYSTEM

---

No lens care system will be used in this study.

#### 4.3.3 LUBRICATING DROPS

---

Participants will not be encouraged to use lubricating drops; however, those who habitually use lubricating drops will be allowed to continue using their normal drops, except for on the day of the screening visit (Visit 1) and on the day of data collection (Visit 2). Lubricating drop use will be recorded at each visit. In the event of an adverse event, lubricating drops may be given to participants.

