#### 4.4.2 VISIT 1: SCREENING

---

All participants who signed the informed consent letter will be assigned a study ID number. The investigator will determine participant eligibility using the inclusion and exclusion criteria. Ineligible participants will be discontinued from the study. The procedures to be performed are outlined below:

- Participants will attend the screening visit having not used any eye drops or artificial tears on the day of the visit.
- The participant will be required to read and sign an Informed Consent Form prior to enrollment. When the participant has signed the consent form, the participant will be considered to be enrolled in the study.
- Participant demographics and medical history (age, sex, current dry eye treatments, medical conditions, medications, allergies)
- Ocular Surface Disease Index (OSDI) questionnaire
- Monocular and binocular logMAR visual acuity will be recorded with high contrast letters under high illumination with spectacles (if necessary).
- Tear meniscus height (OCULUS Keratograph® 5M)
- Non-invasive Keratograph® break up time (OCULUS Keratograph® 5M)
- The investigator will confirm that the participant meets the eligibility specifications set out in the inclusion criteria to be categorized as either a dry eye or non-dry eye participant. Participants who do not meet this criteria will be discharged and will not continue with the remainder of the screening visit.
- Lipid layer thickness (EASYTEAR®view+)
- Assessment of meibomian gland secretion and expression
- Lid margin assessment
- Slit lamp biomicroscopy
- Meibography (OCULUS Keratograph® 5M)
- Anterior eye photographs of each eye will be taken with a slit lamp camera.
- Participants will practice evaporimetry measurements.
- Measurement of volume within the goggle.
- Slit lamp biomicroscopy (safety check).
- Monocular and binocular logMAR visual acuity will be recorded with high contrast letters under high illumination with spectacles (if necessary).
- The investigator will confirm that the participant meets the eligibility specifications set out in the inclusion and exclusion criteria and is eligible to continue with the study.

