#### 4.5.2 MEDICAL HISTORY

---

At the screening visit, medical history questions to determine any current medications, current dry eye treatments, allergies and relevant medical conditions will be asked and documented. At subsequent visits, participants will be asked about changes in their medication or medical condition(s).

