#### 4.5.3 OCULAR SURFACE DISEASE INDEX (OSDI) QUESTIONNAIRE

---

The OSDI is a dry eye questionnaire that asks the participant to reflect and rate their symptoms of eye dryness in different working conditions and environments over the past week. A higher composite score indicates more severe dryness and scores can range from 0 to 100. A score of <13 will be considered asymptomatic and a score  $\geq 13$  will be symptomatic.

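### Criterion 7b sets no condition on drop use, so a person whose one-week OSDI is held below 13 by habitual lubricants can enter as a non-dry eye control

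*Combined protocol and SAP*

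**What the plan says.** **Group definition (4.2.3, criterion 7).** The dry eye group needs OSDI of at least 13 and NIKBUT of at most 5 s in the worst eye. The control rule begins "Non-dry eye participant group: Symptoms: OSDI" and continues with a score below 13 and NIKBUT of at least 10 s in the worst eye. Neither rule mentions drop use.

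**Drop rule.** Inclusion criterion 6 asks that the person "Is willing not to use eye drops or artificial tears on the days of visits 1 or 2". Section 4.4.2 applies this at screening: "Participants will attend the screening visit having not used any eye drops or artificial tears on the day of the visit". On other days, section 4.3.3 provides that "those who habitually use lubricating drops will be allowed to continue using their normal drops, except for on the day of the screening visit"; the sentence then adds the day of Visit 2. The permission is not limited to either group.

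**OSDI window (4.5.3).** Participants "rate their symptoms of eye dryness in different working conditions and environments over the past week".

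**What is recorded.** Under 4.5.2, at screening "any current medications, current dry eye treatments, allergies and relevant medical conditions will be asked and documented". Section 4.3.3 adds that lubricant use is noted at each visit. Neither item enters the group definition or Table 4.

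**Where the groups are used (section 3).** The second hypothesis is that "dry eye participants will have higher baseline rates of tear evaporation compared to non-dry eye participants".

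**The concern.** The two halves of the group definition refer to different treatment states. NIKBUT describes the eye on a day without drops. OSDI describes a week in which a habitual user may have taken drops almost throughout.

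Consider a person whose OSDI would be 13 or more without drops and whose NIKBUT is 10 s or more. Under 7a and 7b that person belongs to neither group. If drops bring the weekly score below 13, the same person satisfies 7b and becomes a control. This does not require any drop effect to last overnight into the visit day.

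What is at stake is the meaning of non-dry eye in Hypothesis 2. The intended comparator is presumably someone free of symptoms without treatment, and the criteria as written do not secure that. With a target of 10 controls, one such participant is a tenth of the group.

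**Working it through.** The plan gives no sample size, power or effect figure, so there is nothing to reproduce. The check is a count of days, a search for a rule that closes the gap, and a bound on the effect.

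**1. Days in the OSDI window on which drops are permitted**

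Inputs: recall of 7 days (4.5.3); drops barred only on visit days (4.2.3 inclusion 6, 4.3.3, 4.4.2); at most one repeat screening (4.2.4).

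| Case | Days permitted |
|---|---|
| Window includes the Visit 1 day | 7 − 1 = 6 of 7 (86%) |
| Window is the seven days before Visit 1 | 7 of 7 |
| Repeat screening in the same week, both visit days in the window | 7 − 2 = 5 of 7 |

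These are days on which use is allowed, not days of actual use.

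**2. Does another rule exclude such a control?**

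- Exclusion 2 (active ocular disease): no. The footnote to 4.2.3 states that dry eye does not count as active disease.
- Exclusion 4 (medications that may affect an outcome): only at the investigator's discretion. It does not name lubricants, and 4.3.3 expressly allows them.
- Exclusion 16 (14-day window): covers drops or treatments in another research study, not a participant's own drops.
- Section 8 (topical ocular medication): concerns use during the study, not the week before screening.

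No mandatory rule closes the gap.

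**3. What the NIKBUT requirement does**

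A control needs a median of three readings (4.5.6) of at least 10 s in the worst eye on a drop-free day. Drop users with unstable tears that day are therefore kept out. Those who can still enter are drop users whose tear film already meets the control sign.

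**4. Bound on the effect**

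Let k of the 10 controls be of this kind, with mean evaporation rate a fraction f of the way from the true control mean to the dry eye mean. The expected group difference is then multiplied by 1 − kf/10. Both k and f are assumptions, since the documents give neither.

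- k = 1: f = 0 gives 1.00; f = 0.5 gives 1 − 0.05 = 0.95; f = 1 gives 0.90.
- k = 2: f = 0 gives 1.00; f = 0.5 gives 0.90; f = 1 gives 0.80.

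Step 3 makes f near 1 implausible, so 0.90 and 0.80 are outer limits, not expected values.

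**5. Comparison with sampling error**

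With 10 per group and SD 1, the standard error of the difference is √(2/10) = 0.45 SD. For an assumed true difference of 1 SD, k = 1 and f = 0.5 shift it by 0.05 SD, and 0.05/0.45 is about one-ninth of a standard error. The outer limit k = 2, f = 1 shifts it by 0.20 SD, which is under half a standard error.

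**The case against.** The strongest reply is that the objective sign already contains the problem. Hypothesis 2 concerns a tear-film measure, and anyone admitted by this route has a drop-free break-up time in the control range. Such a person's evaporation rate may be close to that of any other control, so the effect could be nil. This stands, and it is why the effect can only be called modest.

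Three further points also stand:

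- The documents do not say how many controls would use drops, or whether drops move anyone across the threshold of 13.
- The direction is not settled. On-treatment OSDI also acts on 7a: a drop user enters the dry eye group only if the score stays at 13 or more despite drops. That selects more symptomatic cases and could widen the contrast.
- Drop use and treatments are recorded, so affected controls could be identified afterwards, and an investigator could invoke exclusion 4.

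The last point does not remove the concern. Identification afterwards does not restore a group of 10, and nothing requires the investigator to act when 4.3.3 allows the drops.

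A reader might also infer that a diluted difference would inflate later sample sizes, because section 4.2.1 says "Results from this study will help with sample size determination for future studies" and section 10.1 plans an interim calculation of the final sample size. The documents do not support that step. Neither section ties the sample size to the dry eye versus non-dry eye difference, Table 4 lists no between-group test, and the stated objective is the before-and-after comparison.

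**Conclusion.** The gap is real but minor, and worth considering because it is easily closed. As written, 7b can admit a control whose symptom score was obtained largely on treatment. The consequence is confined to Hypothesis 2, where each such person is 1 of 10 controls. Any loss in the group difference is at most 10% per affected control, and probably well below that given the NIKBUT requirement. If no control uses drops, nothing changes.

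The conclusion rests on the text of 4.2.3, 4.3.3 and 4.5.3 and assumes that some otherwise eligible controls are habitual users.

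It would go too far to read this as dry eye patients being enrolled as controls. A person with NIKBUT of 10 s or more does not meet 7a whatever the OSDI. Nor does it touch the primary comparison of evaporation before and after the drop, which is made within participants.

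**What to change.** Add one clause to criterion 7b: non-dry eye participants do not habitually use lubricating drops or any other dry eye treatment, and have used none in the week before Visit 1. For a repeat screening, the week should be counted back from the visit at which OSDI is scored.

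Leave 7a, the same-day rule, the rescheduling rule in 4.4.3 and exclusion 4 unchanged. With the clause, use in the controls' recall window before the visit is 0 days.

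**Cost.** No new procedure is needed: section 4.4.2 lists medical history, including current dry eye treatments, before the group check. Some drop users with a truly normal tear film will be lost as controls, as will anyone who used a single drop that week, so a few more screenings may be needed within the limit of 60. Dry eye participants may remain on their habitual drops between visits while controls use none. That difference between the groups should be stated when Hypothesis 2 is reported.
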